3. LAY SUMMARY

Aortic stenosis (AS) is a common life-threatening condition, where blood flow out of the heart is restricted by narrowing of the aortic valve. There are two ways to treat AS. Transcatheter Aortic Valve Implantation (TAVI) inserts a new valve inside the existing diseased valve. Surgical aortic valve replacement (AVR) involves surgery on the heart to replace the diseased valve.

TAVI is less invasive than surgical AVR. However, there are still risks with TAVI, including stroke and death, although these are lower than the risks associated with surgical AVR. Stroke in TAVI can be caused by debris released into the bloodstream by the procedure. Devices, called cerebral embolic protection (CEP), have been developed to capture some of this debris. The device is composed of filters which are temporarily placed in the arteries supplying blood to the brain. However, we do not know if the risk of stroke in TAVIs is lower with CEP or without CEP. This trial will allow us to answer this question.

In this study we will randomly assign patients having a TAVI to receive CEP during TAVI or to the current standard of care without CEP. Potential participants will be approached prior to their TAVI procedure to discuss the trial. If they are happy to take part, full informed consent will be sought. Following the TAVI, we will assess whether participants have a stroke in the following 72 hours. We will also assess other ways the CEP treatment impacts on the NHS as well following-up participants for 12 months to assess their long-term outcomes. We will recruit 9712 participants across the UK over 5 years.

4. SYNOPSIS

Trial Title	British Heart Foundation Randomised Trial of Routine Cerebral Embolic Protection in Transcatheter Aortic Valve Implantation
Internal ref. no. (or short title)	BHF PROTECT-TAVI
Trial registration	ISRCTN16665769
Clinical Phase	Phase III
Trial Design	A prospective open-label, outcome adjudicated, multicentre randomised controlled trial (RCT) evaluating the use of a cerebral embolic protection device in participants with aortic valve stenosis planned for treatment by Transcatheter Aortic Valve Implantation (TAVI). Participants will be randomised 1:1 into a treatment group using the cerebral embolic protection device or a control group with no cerebral protection. The primary outcome measure is stroke at 72-hours post-TAVI or hospital discharge (if sooner).
Trial Participants	Subjects with aortic stenosis planned for treatment by a TAVI.
Intervention	The intervention group will have TAVI performed with CEP. The Claret Sentinel dual-filter device (Boston Scientific, MA, USA) is a single use, embolic protection catheter inserted into the right radial or brachial artery. This is the only device currently approved for clinical use in both Europe and the USA. The device employs two filters (nitinol frames with 140-micron pores polyurethane film), one delivered to the brachiocephalic artery (Proximal Filter), and one to the left common carotid artery (Distal Filter) before TAVI. Following the TAVI procedure the system is removed.
Comparator	The comparator (control) group will have TAVI performed without the use of a CEP device (standard of care).
Primary Outcome	The incidence of stroke at 72 hours post-TAVI, or hospital discharge (if sooner)

Secondary Outcome	 Combined incidence of all-cause mortality or non-fatal stroke at 72 hours post-TAVI, or hospital discharge (if sooner) Combined incidence of all-cause mortality, non-fatal stroke or transient ischaemic attack at 72 hours post-TAVI or hospital discharge (if sooner) Incidence of all-cause mortality at 72 hours post-TAVI or hospital discharge (if sooner) Win ratio for all-cause mortality, disabling stroke and non-disabling stroke at 72 hours post-TAVI, or hospital discharge (if sooner) Incidence of all-cause mortality at 12 months post-TAVI Incidence of all-cause mortality up to the end of the trial. This will use trial data up to 12 months, and centrally held NHS data from 12 months to the end of the trial Incidence of stroke as defined by centrally held NHS data (described in section 14.7) between 72 hours post-TAVI or hospital discharge (if sooner) and 30-days post-TAVI Incidence of stroke as defined by centrally held NHS data (described in section 14.7) between 30-days post-TAVI and the end of the trial Stroke severity assessment in participants who have had a stroke within 72-hours post-TAVI or hospital discharge (if sooner) Disability Outcome assessed up to 12 months post-TAVI in participants who have had a stroke within 72-hours post-TAVI or hospital discharge (if sooner) Cognitive Outcome assessed up to 12 months post-TAVI (collection of cognitive outcome data now discontinued; see section 7.2) Vascular access site related complications at 72-hours post-TAVI or hospital discharge (if sooner) and between 6-8 weeks post-TAVI Cost-effectiveness analysis at 12 months post-TAVI
Sample Size	9712
Planned Trial Period	Planned start date: 01 August 2020 Planned end date: 31 August 2027 Total project duration: 85 months Individual participant involvement: 12 months after TAVI procedure
Planned Recruitment period	58 months

5. ABBREVIATIONS

AE	Adverse event
AS	Aortic Stenosis
AVR	Aortic Valve Replacement
CEP	Cerebral Embolic Protection
CI	Chief Investigator
CRF	Case Report Form
DMC	Data Monitoring Committee
HES	Hospital Episode Statistics
HRA	Health Research Authority
ICH GCP	International Conference on Harmonisation Good Clinical Practice
LSHTM CTU	London School of Hygiene and Tropical Medicine Clinical Trials Unit
MHRA Medicines and Healthcare products Regulatory Agency	
MoCA	Montreal Cognitive Assessment
NHS	National Health Service
NIHSS	National Institutes of Health Stroke Score
PI	Principal Investigator
QVSFS	Questionnaire to Verify Stroke Free Status
REC	Research Ethics Committee
SAE	Serious Adverse Event
smRSq	simple modified Rankin Scale questionnaire
SOP	Standard Operating Procedure
TAVI	Transcatheter Aortic Valve Implantation
TIA	Transient Ischaemic Attack

6. BACKGROUND AND RATIONALE

6.1. Background

Aortic stenosis (AS) is a common condition where the valve leading out from the heart (aortic valve) becomes narrowed (stenosed). This causes symptoms such as chest pain, breathlessness and exertional syncope and increases the risk of death. The number of patients with AS is rising as it affects the elderly, who represent an increasing proportion of the population. Treatment of AS can be by Transcatheter Aortic Valve Implantation (TAVI) or surgical aortic valve replacement.

TAVI has become an important treatment option for patients with AS who are at high-risk from surgery, and the evidence supporting its safety and effectiveness in other patient groups is increasing. TAVI is less invasive, leads to faster recovery and is associated with less morbidity than surgical aortic valve replacement. The risks of TAVI include complications from damage to the artery used for the procedure, stroke and death. However, it is likely that TAVI will be used in a wider group of patients as we gain further evidence^{1,2}.

Stroke is an important, but unpredictable complication associated with TAVI, and will become an even more important concern to patients and healthcare funders as TAVI is used for younger patients at lower risk from surgery, and in greater numbers as the proportion of older people increases in the population. Indeed, TAVI patients report that maintaining independence is a more important treatment goal than preventing death³, and other studies show that stroke may be regarded as a worse health-state than death by patients⁴. The majority of TAVI related strokes are ischaemic in nature, presumed due to embolism, and occur early after TAVI ^{5 6}. This suggests they are caused by debris being released into the circulation and reaching the blood supply to the brain (embolism). TAVI-associated stroke leads to prolonged hospital stay, a reduced chance of returning to independence, and a near 6-fold increased risk of death within 30 days ⁸⁻¹⁰. Stroke increases the cost of the index hospitalisation and doubles rehospitalisation costs ¹¹. Reducing the risk of stroke during TAVI has important implications for improving patient outcomes and decreasing healthcare resources.

6.2. Evidence for CEP in TAVI:

The evidence supporting the use of CEP in TAVI is based on three lines of investigation (i) proof-of-principle studies have confirmed that debris is retrieved from the majority of CEP devices when they are examined after TAVI ¹², suggesting that these devices do reduce embolic debris reaching the brain. (ii) Imaging studies using magnetic resonance imaging (MRI) scanning to identify brain injury have confirmed that nearly three quarters of patients had new brain lesions after TAVI, and that use of CEP devices was associated with reduced volume but not number of new lesions ¹³. The significance of these clinically 'silent' lesions in the TAVI population remains uncertain, but they have been associated with cognitive decline and dementia in other studies ¹⁴. (iii) Clinical evidence for the efficacy of CEP includes 4 randomised trials (described below), which were based on brain imaging surrogate endpoints, but also gathered clinical outcomes ¹⁵ ¹⁶ ¹⁷ ¹⁸, 2 clinical case-series ¹⁹ ²⁰, and 2 systematic reviews ^{21,22}. Importantly these studies focussed on surrogate endpoints, were not powered for hard clinical endpoints, have reported outcomes at different times after TAVI, and include a range of CEP devices.

6.3. Previous research in CEP

6.3.1. Randomised Trials

The SENTINEL trial included 363 patients. The primary endpoint was new lesion volume on MRI scans. The study was neutral for an effect of CEP on the imaging endpoint, but did demonstrate a numerical trend toward stroke reduction from 9.1% to 5.6% (p=0.25). The CLEAN-TAVI trial included 100 patients¹⁶. The primary endpoint was based on MRI imaging. There was a reduction in new lesions and volume of lesions in the CEP group, but no reduction in neurological events (10% minor stroke in both groups). The DEFLECT III study, an exploratory study using MRI imaging included 85 patients¹⁷. There was a reduction in the

number of new lesions (21% to 11.5% in the CEP group), and a numerical reduction in in-hospital stroke from 5% to 2%. The MISTRAL-C trial included 65 patients and had an imaging based primary end-point¹⁸. There was a reduction in the proportion of patients with new lesions in the protected areas from 55% to 20% in the CEP group. This was associated with a numerical reduction in major stroke from 7% to 0% in the CEP group.

6.3.2. Observational studies

The University of UIm series was an observational comparison of 280 consecutive patients treated with CEP to a historical propensity matched population. This single centre series demonstrated that stroke rates at 7-days were lower in the CEP group compared with the control group: 1% (4/280) compared with 5% (13/280), odds ratio (OR) 0.29, 95% CI 0.10 to 0.93, p=0.03. Mortality and stroke at 7-days was also significantly lower in patients with CEP than in the control group: 2% (6/280) compared with 7% (19/280), OR 0.30, 95% CI 0.12 to 0.77 (p=0.01).

6.3.3. Systematic reviews

A systematic review and meta-analysis of 1225 patients having TAVI (570 CEP and 655 control) showed that there was no statistical difference between groups for stroke within 72-hours of the procedure, the risk ratio (RR) of 0.53 suggested a potential benefit of cerebral protection (95% confidence interval (CI) 0.27 to 1.07, p=0.08) although the number of events was small (13/335 vs 15/180) and the statistical evidence was weak. More recently a further patient-level pooled analysis has been conducted combining the observational Ulm series and data from the randomised SENTINEL and CLEAN-TAVI trials (N=1306)²³. Propensity matching allowed comparison of 533 patients who underwent TAVI with CEP to 533 without CEP. In patients undergoing TAVI with CEP there was strong evidence that stroke at 72 hours after TAVI and the combination of 72 hour mortality and stroke were reduced (10/533(1.88%) vs. 29/533 (5.44%), OR 0.35, 95% confidence interval (CI) 0.17–0.72, relative risk reduction 65%, p=0.0028 and 11/533 (2.06%) vs. 32/533 (6.00%), OR 0.34, 95% CI 0.17–0.68, relative risk reduction 66%, p=0.0013 respectively). These studies suggest a clinical effect of CEP in reducing early stroke with a number needed to treat of approximately 25. However caution is needed in interpreting these results because of the lack of power and heterogeneity in the included studies²⁴. Indeed, two recent meta-analyses reach different conclusions on the efficacy of CEP highlighting the need to conduct a well-powered randomised controlled trial ^{21,25}.

6.4. Why is the study needed now?

The evidence for the use of CEP has recently been assessed by National Institute for Health and Care Excellence (NICE) interventional procedure guidance committee (IPG 650), which concluded that there are no safety concerns over the use of CEP devices, but that the evidence on efficacy is inconclusive: It encouraged further research particularly to better understand patient selection and risk stratification²⁶. We need high-quality evidence from an adequately powered randomised controlled trial to establish the safety, efficacy and cost-effectiveness of the technique and guide best practice in this important and expanding clinical field. CEP devices are not currently available in the NHS. BHF PROTECT-TAVI offers the unique opportunity within the NHS to test CEP devices in the general population of patients eligible for TAVI.

This trial will address the question of whether the routine use of CEP in TAVI reduces incidence of stroke in patients undergoing TAVI. This is a novel study because it is powered on a single clinically relevant outcome of stroke in an unselected TAVI population. This trial will address an important and unanswered clinical question which may impact future guidelines.

6.5. Stroke risk is not reduced with increasing experience

Increased TAVI volumes and institutional experience have contributed to reduced death and vascular complications, but this is not the case for stroke, which remains independent of experience and volume ²⁷ ²⁸. Although the most recent randomised trials in patients at low surgical risk have suggested that TAVI may be superior to surgery, they were underpowered to detect a difference in stroke rates. Moreover, the

incidence of stroke has not reduced over time in registries of unselected patients. A recent analysis of the TVT registry analysed outcomes from over 100,000 TAVI procedures between 2011-17 and the risk of stroke remained constant over the 6-year period ²⁹. Furthermore, as TAVI is offered to younger and lower-risk patients, the longer term consequences of stroke are even greater over their lifespan given the reported impact on return to work, social activities and finances^{30,31}.

6.6. Stroke risk cannot be accurately predicted

Observational studies have identified the severity of aortic arch atheroma, smaller aortic valve area, degree of valve calcification, procedure time, advancing age, prior stroke, atrial fibrillation and renal impairment as risk factors for TAVI related stroke. The most comprehensive contemporary analysis from the TVT registry of nearly 100,000 procedures has developed a predictive model for TAVI related stroke. This confirmed the importance of prior stroke, age, peripheral vascular disease, chronic kidney disease, and smaller body habitus, but even with this large dataset the best predictive model had a modest predictive value with a C-statistic of only 0.62 ³².

7. OBJECTIVES AND OUTCOME MEASURES

PRIMARY OBJECTIVE	OUTCOME MEASURES & TIMEPOINTS
Does the routine use of CEP devices reduce the incidence of stroke associated with TAVI?	Incidence of stroke at 72 hours post-TAVI, or hospital discharge (if sooner)
SECONDARY OBJECTIVE	OUTCOME MEASURES & TIMEPOINTS
Does the routine use of CEP devices improve stroke, mortality, and cognitive/ disability outcomes?	Combined incidence of all-cause mortality or non-fatal stroke at 72 hours post-TAVI or hospital discharge (if sooner)
	Combined incidence of all-cause mortality, non-fatal stroke or transient ischaemic attack at 72 hours post-TAVI or hospital discharge (if sooner)
	Incidence of all-cause mortality at 72 hours post-TAVI or hospital discharge (if sooner)
	Win ratio for all-cause mortality, disabling stroke and non-disabling stroke at 72 hours post-TAVI, or hospital discharge (if sooner)
	Incidence of all-cause mortality at 12 months post-TAVI
	Incidence of all-cause mortality up to the end of the trial. This will use trial data up to 12 months, and centrally held NHS data from 12 months to the end of the trial
	Incidence of stroke as defined by centrally held NHS data (described in section 14.7) between 72 hours post-TAVI or hospital discharge (if sooner) and 30-days post-TAVI
	Incidence of stroke as defined by centrally held NHS data (described in section 14.7) between 30-days post-TAVI and the end of the trial

	Stroke Severity Assessed using the National Institutes of Health Stroke Scale (NIHSS) in participants who have had a stroke within 72-hours post-TAVI or hospital discharge (if sooner)
	Disability Outcome Assessed using the Simple Modified Rankin Scale questionnaire (smRSq) up to 12 months post-TAVI in participants who have had a stroke within 72-hours post-TAVI or hospital discharge (if sooner)
	Cognitive Outcome Assessed using the standardised Montreal Cognitive Assessment (MoCA) up to 12-months post-TAVI.
	Vascular access site related complications (VARC-2 criteria) at 72-hours post-TAVI or hospital discharge (if sooner) and between 6-8 weeks post-TAVI
Is the routine use of CEP devices costeffective?	Cost-effectiveness analysis at 12 months

7.1. Primary outcome:

7.1.1. Incidence of all stroke at 72-hours after TAVI

The primary outcome is stroke at 72-hours (or at hospital discharge, if sooner) as this is the main clinical outcome that CEP might influence. From a mechanistic perspective, CEP will only impact on procedure-related embolic stroke.

7.1.2. Stroke and Transient Ischemic Attack definitions

Stroke will be defined as a new or worsened focal or global neurological deficit of presumed vascular origin, either ischaemic or haemorrhagic, occurring after randomisation and persisting for greater than 24 hours or leading to death. In this definition, a new stroke will not be defined exclusively by brain imaging, and a clinical deficit must be present for greater than 24 hours³³. This will ensure a consistent definition of stroke across all enrolling sites not driven by the different availability of MR imaging in particular. In anticipation of changes in NHS Stroke Care Pathways over the lifetime of the trial, the definition of stroke will include those who have a mechanical thrombectomy for acute ischaemic stroke according to contemporary National Guidelines³⁴. Patients who have identified occlusion of the cerebral vessels and undergo mechanical thrombectomy within 72-hour period after TAVI will be considered to have had a stroke outcome. This additional definition of stroke will allow the capture for the primary outcome of a small number of patients that have a complete neurological recovery as a result of that mechanical thrombectomy, and, therefore, will not meet the first definition.

Patients with a clinical deficit lasting less than 24 hours in duration, regardless of imaging evidence of infarction in the relevant vascular territory, will be defined as having a Transient Ischaemic Attack for the purposes of the secondary outcome analysis.

In keeping with other recent large clinical trials, stroke outcome ascertainment will be maximised by use of the validated 8-item question Questionnaire to Verify Stroke Free Status (QVSFS) on a daily basis in the 72 hours following the procedure, in addition to routine clinical review³⁵⁻³⁷. An answer of YES on the QVSFS since the procedure will prompt a local outcome assessment against the stroke definition as described above. The clinical diagnosis of stroke will be defined by local pathways including the stroke team as appropriate.

Initial stroke severity will be quantified by the National Institutes of Health Stroke Score (NIHSS), but a change score of 0 may still be compatible with a new stroke (for instance, a stroke causing a new deficit in the hand alone would score 0 on the NIHSS)³³.

The recovery and/or ongoing disability following stroke will be quantified using the modified Rankin Scale (mRS), the standard measure for assessing post-stroke disability. Sites will use the simple modified Rankin scale questionnaire (smRSq) preferably face-to-face to determine the mRS³⁸. The advantage of this approach is that it may also be captured via postal questionnaire, or via telephone interview, thus minimising the likelihood of missing outcome data³⁹.

7.1.3. Adjudication of Primary outcome

The outcomes at 72-hours will be adjudicated by an independent Clinical Events Committee (CEC) using a standard protocol to limit bias (see section 17.3). The CEC will be blinded to trial treatment.

In addition to adjudicating the stroke outcomes, the CEC will be asked to identify a systematic approach to the identification of periprocedural hypotension so that its contributory role to any stroke outcome may be consistently applied. While most are expected to be embolic, there will be a small number of patients who have haemodynamic events for instance, following peri-procedure cardiac arrest. Any difference in stroke mechanism between the arms of the trial will be explored in the secondary analyses.

7.2. Key Secondary outcomes

- **1.Combined incidence of all-cause mortality or non-fatal stroke** at 72 hours post-TAVI or hospital discharge (if sooner). Stroke will be assessed as defined in section 7.1.2.
- **2.** Combined incidence of all-cause mortality, non-fatal stroke or transient ischaemic attack at 72 hours post-TAVI or hospital discharge (if sooner).
- 3. Incidence of all-cause mortality: at 72 hours post-TAVI or hospital discharge (if sooner)
- **4**. **Win ratio for all-cause mortality, disabling stroke and non-disabling stroke** at 72 hours post-TAVI, or hospital discharge (if sooner)
- 5.Incidence of all-cause mortality: at 12 months post-TAVI.
- **6. Incidence of all-cause mortality:** up to the end of the trial. This will use trial data up to 12 months, and centrally held NHS data from 12 months to the end of the trial
- **7.** Incidence of stroke as defined by centrally held NHS data (described in section 14.7): Identified between 72 hours post-TAVI or hospital discharge (if sooner) and 30-days post-TAVI.
- **8.** Incidence of stroke as defined by centrally held NHS data (described in section 14.7): Identified between 30-days post-TAVI and the end of the trial.
- **9. Stroke Severity:** In participants who had a stroke within 72-hours post-TAVI or hospital discharge (if sooner) will be assessed using the National Institutes of Health Stroke Scale (NIHSS). This measure has been adopted as a secondary outcome to explore the association between use of the CEP and prevention of large cerebral vessel occlusion (LVO). Strokes with an NIHSS score of 10 or greater will be defined as severe.
- **10. Disability Outcome:** Stroke recovery and/or ongoing disability in participants who had a stroke within 72-hours post-TAVI or hospital discharge (if sooner) will be assessed with the smRSq at discharge and between 6-8 weeks post-TAVI and at 12-months post-TAVI.
- **11. Cognitive Outcome:** The standardised Montreal Cognitive Assessment (MoCA) detects mild cognitive impairment (MCI). It will be collected pre-procedure to establish the baseline measure. The telephone MoCA (without the items requiring the use of a pencil and paper or visual stimulus) is a valid and sensitive means of testing cognition following stroke and TIA. However, it is unable to measure visuoexecutive items; and, the performance of some domains (repetition, verbal fluency, and abstraction) performs less well over the telephone than with a face-to-face administration. However, it offers the opportunity to maximise the capture of this outcome assessment should face-to-face assessment prove not to be practical. Cognitive outcomes will be assessed up to 12 months post-TAVI.

The MoCA was collected from the start of recruitment in October 2020 and was discontinued from Version 5.0 of the protocol. The analysis for this outcome will be undertaken using all MoCA data collected until the implementation of Protocol Version 5.0.

12. Incidence of vascular access site related complications: Vascular complications will be recorded according to standard criteria defined by the Valve Academic Research Consortium (VARC-2) at 72-hours

post-TAVI or hospital discharge (if sooner) and between 6-8 weeks post-TAVI. Please go to http://onlinejacc.org/content/60/15/1438 for full details or see Appendix C⁴³.

13. Cost-effectiveness analysis: Data on quality of life and resource utilisation will be collected for a formal cost-effectiveness analysis. The validated EQ-5D-5L questionnaire will be used to assess quality of life.

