10.8.1. In hospital

This will be carried out daily up to and including 72 hours post-TAVI, or until discharge if sooner.

Primary outcome

- Stroke status
 - Assessed by routine clinical assessment post-TAVI, supported by the framework provided by the QVSFS.
 - If after routine clinical assessment, the participant is reviewed by the local stroke team, a Stroke Form must be completed.
 - o If the participant answers YES to any of the questions on the QVSFS, this will prompt a local outcome assessment against the stroke definition described in section 7.1.2. and the diagnosis will be recorded on the Stroke Form in the eCRF, with supporting information as required. If a stroke is diagnosed by the stroke team, severity is assessed using NIHSS and recovery is assessed using smRSq
 - Short questionnaires administered for the study

Secondary outcomes

- Mortality status
 - Taken from patient notes
- Vascular injury
 - Taken from patient notes

- Safety reporting
 - Taken from patient notes

The API Study

The API Study Questionnaire is only completed by participants who have consented to take part in the API study (see Section 12). The questionnaire is self-administered and should be completed following the patient's TAVI procedure up to 72 hours post-TAVI or hospital discharge (if sooner).

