10.8.2. Visit 1 – 6-8 weeks post-TAVI

This will be conducted by telephone for the study, however if there is a pre-scheduled clinical visit, it can be done in person.

Contact with the patient will be arranged by a delegated member of the research team at the local hospital. Phone calls are projected to take no more than 10 minutes to complete the EQ-5D-5L questionnaire. The staff contacting the patient will check electronic records prior to contacting the patient to ensure they have not died. While participant preferences for contact will take priority, we advise that after 3 unsuccessful attempts to reach the patient no further attempts are made.

Secondary outcomes assessed:

- Mortality status
 - Taken from patient notes
- smRSq
 - Short questionnaire administered for the study (only done in presence of a stroke outcome)
- EQ-5D-5L
 - Short questionnaire administered for the study
- Vascular injury
 - Taken from patient notes
- Safety reporting
 - Taken from patient notes

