To assess long-term stroke and mortality outcomes, we will link trial participants recruited at NHS sites to Hospital Episode Statistics (HES) and mortality data held by NHS England other central UK NHS bodies and the Office for National Statistics (ONS). Participant's NHS number and their date of birth or their Community Health Index will be shared securely between the London School of Hygiene & Tropical Medicine/University of Oxford and NHS England/other central UK NHS bodies /Office for National statistics (ONS) via secure email in order to request the health outcome data of participants. NHS England/other central UK NHS bodies /ONS will return the requested information to the London School of Hygiene & Tropical Medicine/University of Oxford in pseudo-anonymised form which is only identifiable to the data controller. The data will be held in a secure database on the server at the London School of Hygiene and Tropical medicine. Researchers at the University of York and The Newcastle upon Tyne Hospitals NHS Foundation Trust will be given access to the secure server to undertake analyses for the trial.

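### The early mortality outcome stops at hospital discharge, so a death after discharge but within 72 hours of TAVI is not counted in it

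*Protocol*

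**What the plan says.** Section 7.2 lists four early secondary outcomes that include death: death or non-fatal stroke (item 1), death, non-fatal stroke or TIA (item 2), death alone (item 3), and a win ratio with death listed first (item 4). All four close at 72 hours or at discharge, whichever is earlier. Item 3 reads "Incidence of all-cause mortality: at 72 hours post-TAVI or hospital discharge (if sooner") and item 2 reads "Combined incidence of all-cause mortality, non-fatal stroke or transient ischaemic attack at 72 hours post-TAVI or hospital discharge (if sooner"). The synopsis and the section 7 table use the same window; the table has "Incidence of all-cause mortality at 72 hours post-TAVI or hospital discharge (if sooner").

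On data collection, section 10.8.1 says of the in-hospital assessments: "This will be carried out daily up to and including 72 hours post-TAVI, or until discharge if sooner". Mortality status is listed there, then again at 6-8 weeks (10.8.2) and 12 months (10.8.3), taken from patient notes. Its row in the section 10.6 table carries no stroke-only footnote. Before the 6-8-week call, "The staff contacting the patient will check electronic records prior to contacting the patient to ensure they have not died". Section 14.7 adds central linkage: "we will link trial participants recruited at NHS sites to Hospital Episode Statistics (HES) and mortality data".

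For stroke, item 7 covers the time after the early window, since it counts events "Identified between 72 hours post-TAVI or hospital discharge (if sooner) and 30-days post-TAVI". No outcome does the same for death; the next mortality outcome is at 12 months (item 5).

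**The concern.** The primary outcome's window was carried over to death without a stated reason. Stroke is found by the daily questionnaire and clinical review, which end when the participant goes home. Death can be established later from records that the trial already plans to consult.

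Two things follow. An outcome that readers will take as 72-hour mortality is in fact mortality over a window that varies between participants and depends on discharge practice. And the end of that window is a decision made after randomisation by hospital staff who, under section 10.5, know the allocation. If the arms differed in length of stay, time at risk of a counted death would differ too. A fixed 72-hour window makes the question moot for item 3.

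Safety reporting does not fill the gap. Death is on the section 13.4.1 list of recognised complications, and section 13.2 does not require these to be reported after discharge.

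**Working it through.** **1. What happens to a death at home on day 2 after discharge on day 1**

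| Outcome (section 7.2) | Window for death | Counted? |
|---|---|---|
| Items 1, 2, 3, 4 | to 72 h, or discharge if sooner | No |
| Item 5 | to 12 months | Yes |
| Item 6 | to end of trial | Yes |

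No other section overrides the window for items 1 to 4.

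**2. The plan's own figures (section 14.2)**

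Inputs: 3% versus 2%, two-sided 5%, 80% power, 1:1 allocation, 1% losses. With pooled variance and no continuity correction,

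n per arm = [1.960 × √(2 × 0.025 × 0.975) + 0.842 × √(0.03 × 0.97 + 0.02 × 0.98)]² / 0.01² = 3826 (rounded up),

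so the total is 7652, and 7652 / 0.99 = 7730. Both match the protocol. The point disputes neither, and neither depends on the mortality window. For the death-or-stroke composite (4.2%, risk ratio 0.67), power at 7730 is 91.2%.

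**3. How many deaths the rule might leave out**

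The protocol gives neither length of stay nor the timing of deaths, so every input except 9712 is an assumption.

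Deaths not counted = 9712 × share discharged before 72 h × days of window lost × daily hazard after discharge

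- Low: 9712 × 0.30 × 1 × 0.0002 = 0.6
- Middle: 9712 × 0.50 × 1.5 × 0.0005 = 3.6
- High: 9712 × 0.70 × 2 × 0.0010 = 13.6

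For scale, the section 14.2 planning rates imply 4.2% − 3.0% = 1.2% early deaths without stroke. At that control rate throughout, 9712 × 0.012 ≈ 117, so the middle case is 3.6 / 117 ≈ 3%. The 4.2% is itself only an example in section 14.2.

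**4. Effect on composite power**

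Let f be the assumed share of death-only events that fall after discharge. The counted control rate is 3.0% + 1.2% × (1 − f), with the risk ratio held at 0.67.

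| f | Control deaths not counted (of 4856) | Power, N = 7730 | Power, N = 9712 |
|---|---|---|---|
| 0 | 0 | 91.2% | 96.0% |
| 5% | 2.9 | 90.8% | 95.8% |
| 10% | 5.8 | 90.4% | 95.5% |
| 20% | 11.7 | 89.5% | 95.0% |
| 30% | 17.5 | 88.5% | 94.4% |

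If CEP reduces stroke only (3% to 2%) and leaves death at 1.2% in both arms, the direction reverses. Power at 9712 rises from 74.2% (f = 0) to 75.6% (f = 10%), because the uncounted deaths carry no treatment effect. Power is therefore no argument either way.

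**5. What unequal discharge could do to item 3**

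Suppose true 72-hour mortality is equal, but 10% of early deaths in one arm and 20% in the other fall after discharge. The observed risk ratio is then (1 − 0.10) / (1 − 0.20) = 0.90 / 0.80 = 1.125 instead of 1.00. With equal shares it stays at 1.00. This shows the mechanism only.

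**The case against.** The window is explicit, used consistently in the synopsis, the section 7 table and section 7.2, and identical to that of the primary outcome. A reader might infer a contradiction from section 14.2, which describes the composite as measured at 72 hours with no mention of discharge. Section 14.1 shortens the primary outcome in the same way, so this is shorthand. The point concerns a design choice, and that part of the objection stands.

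A reader might also want the fixed window to replace the present one in all four outcomes. The objection to that stands too. In items 1, 2 and 4, a participant discharged on day 1 would stay at risk of death to 72 hours but not of stroke or TIA. A fatal stroke at home would count as a death and a disabling one would not count. In the win ratio the tiers would cover different follow-up. The argument is clean only for item 3.

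Other strong readings fail on the text:

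- *These deaths are lost to the trial.* They count in items 5 and 6.
- *Vital status is known for everyone.* Withdrawal options 2 and 3 (section 10.10) end collection. Central linkage covers NHS sites only, while section 21.2 provides for recruitment at private hospitals. Recording of the date of death is not stated.
- *Early mortality will be biased between arms.* Nothing in the protocol shows that discharge differs by arm. Section 10.7 puts the added procedure time at about 5 minutes.

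What survives is that the protocol gives no reason for ending item 3 at discharge, while later mortality checks are already scheduled.

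**Conclusion.** The point holds as a minor improvement to one secondary outcome, with a matching sensitivity analysis for three others. As written, item 3 is mortality to discharge or 72 hours, and the end of observation is a post-randomisation event decided by unblinded staff. The protocol's own follow-up schedule should allow a fixed 72-hour window without a new visit, provided the date of death is recorded.

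The size is probably small and cannot be derived from the protocol. The range of about 1 to 14 deaths rests wholly on assumed discharge shares, days lost and hazards. A difference in length of stay between arms is possible but not documented. The primary outcome and the sample size are unaffected.

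**What to change.** 1. In section 7.2 item 3, the synopsis and the section 7 table, define early mortality as death from any cause within 72 hours of TAVI, whether or not the participant has been discharged.
2. Take the date of death from the 6-8-week and 12-month status checks, and confirm that the case report form records it. Use linked records for NHS-site participants where available. Say so explicitly, because item 6 at present names central data only for the period after 12 months.
3. Keep the common window for items 1, 2 and 4. Add a sensitivity analysis that counts all deaths to 72 hours, and state that stroke and TIA still stop at discharge in it.

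Cost: a small wording change to one secondary outcome in three places, made through the amendment process, and a little more analysis. No new visit is needed. Participants whose withdrawal ends data collection will still have no later vital status, and the report should give their number by arm.
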